6.6.5 Safety Analyses

There will be no imputation of data for safety analyses.

6.6.6 Missing dates

Adverse event data

Missing or partial date information for AEs will be replaced according to general Boehringer Ingelheim (BI) rules described in the BI guidance for handling of missing and incomplete AE dates (2).

Partial onset dates from clinical event committee (CEC):

In the unlikely case that only the year is documented, the day and month will be imputed as 01 Jan unless the subsequently derived date is before randomisation; in this case the date of randomisation will be used as start date.

If year and month is present the day will be imputed as first of the month unless the subsequently derived date is before randomisation; in this case the date of randomisation will be used.

Death date

For patients with a record of death captured on the electronic case report form (eCRF) with missing or only partial death date from all available sources, the death date will be derived as the latest date of any dates as of: event onset and end dates from either the AE page, or CEC adjudicated onset dates, by using also imputed AE dates, range or of possible days based on partial death date and date of last contact.

Missing information on the date of first administration of trial drug

If the date of first drug administration is missing but the patient was randomised, the date of the first drug administration will be set to the date of randomisation. If the date of first administration is partially missing with the month and year present, the day will be set to the date of randomisation if randomisation was in the same month. If randomisation was in the month prior to the first drug administration the missing day will be imputed as the first day of the month.

Missing date of last contact date:

If the date is partially or completely missing, use the minimum of the following dates:

- the date of Informed Consent (IC) withdrawal (if applicable)
- date of death
- If the patient did not die and did not withdraw consent, the latest of:
 - visit end dates,
 - drug administration dates,
 - last drug stop date,
 - last assessment date (ECG date, date of KCCQ, date of CHQ)
 - AE onset and AE end dates
- (in case for partially missing date) Last day of the year/month given as partial date

In case of a partially missing date, if the imputed date is before the first day of the month/year given as partial date, the first day of the month/year will be used.

All other cases need to be assessed by the trial team on an individual patient basis, using the above points as guidance.

Missing information on the date of trial medication stop

If the date is partially or completely missing, use the minimum of the following dates:

- End of treatment visit date (if available)
- Date of death (if applicable)
- Trial completion (last contact date)
- Longest treatment duration (assuming 1 tablet/day)
- (in case for partially missing date) Last day of the year/month given as partial date

In case of a partially missing date, if the imputed date is before the first day of the month/year given as partial date, the first day of the month/year will be used.

All other cases need to be assessed by the trial team on an individual basis, using the points above as guidance.

Missing information on concomitant therapy dates

For incomplete date information the midpoint of the possible interval will be used. If only the year is present the day and month will be imputed as 01 July, if year and month is present the day will be imputed as 15. If the year is missing, the date will be considered missing.

If this leads to contradictions for the start or end date of a concomitant therapy (e.g. imputed end date before documented start date) a partial end date will be imputed as the end of the interval or a partial start date will be imputed as the start of the interval in the database to resolve this contradiction.

All other cases or conflicting cases resulting from these imputation rules need to be assessed by the trial team on an individual basis.

6.7 BASELINE, TIME WINDOWS AND CALCULATED VISITS

For serum creatinine and values based upon this measurement such as eGFR, baseline will be defined as the mean of all available measurements from the screening visit until start of randomised trial medication. For all other endpoints, baseline will be defined as the last available measurement before start of randomised trial medication.

Since the protocol specifies that all measurements are taken at visit 2 before any intake of trial medication, all measurements at the first day of drug intake are assumed to qualify as baseline measurements. For laboratory values, clock time is recorded. If a lab measurement is done after treatment start, this will not qualify as baseline measurements, except in case of HbA1c, which is considered to be a stable measurement and qualifies for baseline on the whole day of first treatment intake.

For randomised patients without any treatment intake: For serum creatinine and values based upon this measurement such as eGFR, baseline will be defined as the mean of all available measurements from the screening visit until and including the day of randomisation. For all other endpoints, baseline will be defined as the last available measurement before or on the day of randomisation.

Medication taken at baseline is any medication with start date continued or before date of first study medication intake (randomisation for patients not treated) and end date continued or on or after date of first medication intake (randomisation for patients not treated).

Measurements taken after the first intake of randomised trial medication will be considered on-treatment values if they have been obtained up to end of the parameter specific follow-up period as defined in [Table 6.7: 1](#) below and will be assigned to the randomised study drug for efficacy and safety analyses.

Measurements taken after the end of the endpoint specific follow-up period after the last intake of study drug will be considered post-treatment values.

On-treatment (for OC-OT analysis) or all post-randomisation (for OC-AD analysis) efficacy and safety measurements will be assigned to visits based on time windows around the planned visit dates. These time windows are defined based on the planned number of days after the date of first administration of study drug.

The time window for the first visit after randomisation starts on the day after the first intake of study drug. For the primary analysis of the primary endpoint and the key secondary endpoints, the start of the time window of week 12 assessment will follow the protocol defined time window (refer to [Table 6.7: 1](#) for details). For all sensitivity analyses and all other endpoints the midpoint between two on-treatment visits defines the end of a time window, with the midpoint being included in the time window of the preceding visit ([Table 6.7: 2](#)).

Table 6.7: 1 Time windows for primary analysis of primary and key secondary endpoints and Sensitivity analyses using Wilcoxon model

| Visit number | Visit label | Planned days | Time window (days after baseline) | |
|--------------|-----------------------|--------------|-----------------------------------|------------------|
| | | | Start | End |
| 2 | Baseline ¹ | 1 | NA | +1 |
| 3 | Week 6 | 43 | +2 | +77 ² |
| 4 | Week 12 | 85 | +78 | NA ² |

¹ Only values taken prior or on the day of treatment start with randomised study drug can be considered baseline values. To be conservative, all data on the day of treatment start will be assumed to be before treatment start for 6MWT and PROs. Time windows will be used for assignment of measurements to scheduled visits.

² For patients with no value in the visit 4 window (visit 3 window respectively), determination of imputation categories will be: deaths before day 92 (day 77 respectively) will be considered for imputation category 3; value for patients with clinical event overlapping at least partially with the time window day 78 to day 92 (day 2 to day 77 respectively) will be imputed according to imputation category 2.

Table 6.7: 2 Time windows for measurements except primary analysis of primary and key secondary endpoints [OC-OT]

| Visit number | Visit label | Planned days | Time window (days after baseline) | |
|---|-----------------------|-------------------|-----------------------------------|-----------------------|
| | | | Start | End |
| Endpoints assessed at each on-site visit (e.g. creatinine / eGFR) | | | | |
| 2 | Baseline ¹ | 1 | NA | +1 |
| 3 | Week 6 | 43 | +2 | +64 |
| 4 | Week 12 | 85 | +65 | Trt stop + x* days |
| FU | FU | Trt stop + 7 days | Trt stop + x* + 1 day | NA |
| Endpoints that are not assessed on visit 3 (e.g. weight) | | | | |
| 2 | Baseline ¹ | 1 | NA | +1 |
| 4 | Week 12 | 85 | +2 | Trt stop+ x* days |
| FU | FU | Trt stop + 7 days | Trt stop + x* + 1 day | NA |

¹ Only values taken prior to the start of treatment with randomised study drug can be considered baseline values. Time windows will be used for assignment of measurements to scheduled visits.

* see [Table 6.1: 2](#)

Table 6.7: 3 Time windows for measurements except primary analysis of primary and key secondary endpoints [OC-AD]

| Visit number | Visit label | Planned days | Time window (days after baseline) | |
|---|-----------------------|--------------|-----------------------------------|-----|
| | | | Start | End |
| Endpoints assessed at each on-site visit (e.g. creatinine / eGFR) | | | | |
| 2 | Baseline ¹ | 1 | NA | +1 |
| 3 | Week 6 | 43 | +2 | +64 |
| 4 | Week 12 | 85 | +65 | NA |
| Endpoints that are not assessed on visit 3 (e.g. weight) | | | | |
| 2 | Baseline ¹ | 1 | NA | +1 |
| 4 | Week 12 | 85 | +2 | NA |

¹ Only values taken prior to the start of treatment with randomised study drug can be considered baseline values. Time windows will be used for assignment of measurements to scheduled visits.

For examinations that are not planned at every on-treatment visit, the time windows will be defined according to the same algorithm, based on the midpoint between the planned visit day of such an examination. Examples for eGFR and weight can be found in [Table 6.7: 2](#) for OC-OT analyses and in [Table 6.7: 3](#) for OC-AD analyses.

Only one observation per time window will be selected for analysis at an on-treatment visit – the value will be selected which is closest to the protocol planned visit day.

For the primary endpoint (6MWT) and any measurement related to the 6MWT assessment the longest walking distance for each day will be used for the analysis for that day.

If there are two measurements which have the same time difference in days to the planned day, or if there are two measurements on the same day (endpoints not related to the 6MWT), the first value will be used.

Baseline definition for concomitant therapies

Concomitant medication taken at baseline is any medication with start date continued or before date of first study medication intake (randomisation date will be used for patients not treated) and end date continued on or after date of first study medication intake (randomisation date will be used for patients not treated).

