5. A 12-lead ECG will be performed at screening and EOT visits. For this 12-lead ECG, the interpretation of the tracing must be made locally by the investigator or designee. In case of any cardiac symptom (indicating rhythm disorders or cardiac ischaemia), additional 12-lead ECG(s) should be done and any abnormal findings will be reported as AEs.
6. An echocardiogram should be performed on all patients at Visit 1 to assess left ventricular ejection fraction (LVEF) for eligibility.

7. 6MWT to be performed by qualified and experienced personnel. The assessments should be performed by the same qualified and experienced personnel at all visits, where possible. Testing of the 6MWT at each clinic visit should be preferably performed about the same time of day to minimize intraday variability. Prior to performing the 6MWT, the relative contraindications to exercise should be assessed as per [appendix 10.1.3](#). Heart rate and blood pressure will be measured before exercise, at end-exercise, five minutes after termination of exercise and when, for clinical reasons, it is required.
8. One 6 minute walk test (6MWT) will be performed at the screening visit. The 6MWT will be performed after vital signs have been captured and prior to any other study procedures at this visit. If the distance walked is > 350m the patient will be considered a screen failure.
9. Two 6 minute walk tests will be performed at visits 2 and 4 at least 1 hour apart. The largest distance measured will be used for the analysis. If at Visit 2 the distance walked on any test is > 350m or the largest distance walked is < 100m the patient will be considered a screen failure.
10. For the order of completion of patient reported outcome measures please refer to [section 6.2.2](#).
11. Patients who prematurely discontinue from trial medication will be required to return to the study site as soon as possible after treatment discontinuation for the early discontinuation visit and the follow up visit. In addition, the patient should return to clinic for their regularly scheduled week 12 study visit as outlined in [section 3.3.4.1](#).

TABLE OF CONTENTS

TITLE PAGE	1
CLINICAL TRIAL PROTOCOL SYNOPSIS	2
FLOW CHART	7
TABLE OF CONTENTS	10
ABBREVIATIONS	14
1. INTRODUCTION.....	17
1.1 MEDICAL BACKGROUND.....	17
1.2 DRUG PROFILE	18
1.3 RATIONALE FOR PERFORMING THE TRIAL	19
1.4 BENEFIT - RISK ASSESSMENT.....	20
2. TRIAL OBJECTIVES AND ENDPOINTS.....	24
2.1 MAIN OBJECTIVES, PRIMARY AND SECONDARY ENDPOINTS.....	24

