6.6.3 Secondary endpoints

Handling of missing data for the change from baseline to week 6 in exercise capacity as measured by the distance walked in 6 minutes will be analogous to the primary endpoint, see [Table 6.6.3:1](#)

Table 6.6.3: 1 Imputation rules for missing exercise capacity at week 6

| | Category | Ranking | Case description | Imputed change from baseline in 6MWT for described case (in m)* |
|---|---|--|---|---|
| 1 | Missing data on 6MWT at week 6 and no clinical event: Patients with missing 6MWT at week 6 and no event as in category 2 or 3 | Ranked above patients who died or patients with a clinical event, but below patients with available measurement at week 6. | No information of post-baseline 6MWT distance and no clinical event | -354 |
| 2 | Missing data and clinical event (except death). A clinical event is defined as ongoing SAE or AE leading to treatment discontinuation and patient is alive at week 6 | Ranked above patients who died, but below patients with missing data and no clinical event. | Patient has ongoing SAE or AE leading to treatment discontinuation, no information of week 6 6MWT distance and patient alive at week 6. | -356 |
| 3 | Patient died before the measurement of 6MWT at week 6 was conducted. | Ranked by time to death from randomisation | Patient died y days after randomisation | $-358+y/1000$ |

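### The Week 6 walk-test window opens on day 2, so one early-discontinuation walk can count as a measured Week 6 result and displace the death and clinical-event ranks

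*SAP*

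**What the plan says.** SAP Section 6.7 sets the opening of the first post-baseline window: "The time window for the first visit after randomisation starts on the day after the first intake of study drug". Week 6 (planned day 43) therefore runs from day 2 to day 77 in Table 6.7:1, and from day 2 to day 64 in Tables 6.7:2 and 6.7:3. Within a window, "the value will be selected which is closest to the protocol planned visit day"; no earliest day is set.

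Footnote 2 of Table 6.7:1 says who receives a worst-case rank: "For patients with no value in the visit 4 window (visit 3 window respectively), determination of imputation categories will be" as listed there, with deaths in category 3 and clinical events in category 2. Table 6.6.3:1 describes the Week 6 categories. Category 2 reads "Patient has ongoing SAE or AE leading to treatment discontinuation, no information of week 6 6MWT distance and patient alive at week 6", and category 3 reads "Patient died before the measurement of 6MWT at week 6 was conducted". SAP Section 6.6.3 calls this handling analogous to that of the primary endpoint.

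Protocol Section 3.3.4.1 places the early discontinuation visit as soon as possible after stopping, and Section 5.1.1 includes one walk test at it. Flow Chart footnote 11 then adds: "In addition, the patient should return to clinic for their regularly scheduled week 12 study visit". It does not name Week 6.

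For endpoints not taken at Visit 3, the Week 12 rows read "4 | Week 12 | 85 | +2 | Trt stop+ x* days" (Table 6.7:2) and "4 | Week 12 | 85 | +2 | NA" (Table 6.7:3).

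**The concern.** A walk in the first days after randomisation is not a Week 6 measurement, yet the window treats it as one. Once it counts as a value, the patient leaves the imputation table. Two patients with the same course, for example an adverse-event stop on day 8 and death on day 30, are then ranked quite differently depending only on whether they walked at the discontinuation visit. The primary endpoint is built to prevent exactly this.

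At stake is the meaning of a named secondary endpoint: whether its ranking of early deaths and adverse-event stops follows the worst-case strategy the plan sets out.

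**Working it through.** **1. Window arithmetic.** Planned days are 43 and 85, with ± 7 days (Flow Chart).
- Midpoint of the two visits: (43 + 85)/2 = 64. This is the Week 6 end in Tables 6.7:2 and 6.7:3.
- Protocol start of Week 12: 85 − 7 = 78. This is the Week 12 start in Table 6.7:1.
- The same rule for Week 6: 43 − 7 = 36. The SAP uses day 2, which is 43 − 2 = 41 days before the planned day. Day 2 comes from neither the protocol tolerance nor a midpoint, since (1 + 43)/2 = 22.

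**2. The same patient in the two analyses.** Take a patient who stops on day 8, walks once on day 10 and never walks again.

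| Course | Week 6 as written | Week 12 primary (Protocol Table 7.5:1) |
|---|---|---|
| Dies on day 30 | measured change, ordinary rank | −358 + 30/1000 = −357.970 |
| Alive, qualifying clinical event | measured change, ordinary rank | −356 |
| Alive, no clinical event | measured change, ordinary rank | −352 + x/1000 |

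Without the day-10 walk, the first patient would also receive −357.970 at Week 6. Table 6.6.3:1 has no row for a last available value, because the day-2 start leaves nobody to whom such a row could apply.

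**3. Reproducing the plan's figures.** Inputs from Protocol Section 7.7: difference 30 m, SD 72 m, two-sided 0.05, power 90%, 150 per group.
- P(X<Y) = Φ(−30/(72√2)) = 0.384. Noether's formula, (1.960 + 1.282)² / [12 × 0.25 × (0.384 − 0.5)²] / 2, with P unrounded gives 130.5, so 131 per group as stated.
- Simulated Wilcoxon power with 5%, 8% and 10% ranked worst in each arm: 90.3%, 87.2% and 84.8%. The protocol gives 90%, 87% and 85%.

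**4. Effect per patient.** The SD of the rank sum is √(150 × 150 × 301/12) = 751. Moving one patient from a middle rank to the bottom changes the rank sum by about 75, so z moves by 75/751 ≈ 0.10 for each net patient between arms.

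**5. Illustration for Week 6.** The stop rates, a Week 6 effect of 30 m, and early changes distributed as N(0, 72) or N(−40, 72) are assumptions. Every stopper is taken to have only an early walk, and to rank worst if that walk is not used. Entries are power in favour of empagliflozin.

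| Stops, empagliflozin / placebo | Early walk kept, mean 0 | Early walk kept, mean −40 | Ranked worst |
|---|---|---|---|
| 5% / 5% | 91.7% | – | 90.3% |
| 8% / 8% | 89.5% | – | 87.2% |
| 10% / 10% | 88.3% | – | 84.8% |
| 8% / 2% | 90.3% | 83.1% | 61.9% |
| 2% / 8% | 93.1% | 95.7% | 98.8% |

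With balanced stops the gaps are 1.4, 2.3 and 3.5 points, and the rule as written has the higher power. With 8% against 2% the gap is 28.4 or 21.2 points. With the arms reversed it is 5.7 or 3.1 points the other way.

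**6. Endpoints not taken at Visit 3.** Weight is named. Haemoglobin and haematocrit follow, because Flow Chart footnote 4 leaves them out of the Visit 3 panel and SAP Section 6.7 applies the same algorithm. Day 2 is 85 − 2 = 83 days before the planned Week 12 day. The midpoint with baseline would be (1 + 85)/2 = 43.

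**The case against.** The strongest reply is that little depends on this. The Week 6 walk is outside the testing hierarchy (SAP Section 7.5.2), and a walk nearer day 43 displaces the early one. Protocol Section 3.3.4.1 asks for every effort to keep stoppers at their scheduled visits. Using off-treatment values is deliberate, so a patient who stopped for an adverse event and has a genuine Week 6 walk should be ranked on it. SAP Section 6.6 scores an attended visit without a walk as 0 m; if that carries over to Week 6, patients too ill to walk do not receive a middle rank. The missing last-available-value row may even show that the authors meant any early walk to count.

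Most of this stands and limits the point. It does not remove it. The only return visit named for stoppers is Week 12, so the early walk may be the only one in the Week 6 window. Using off-treatment values does not make a day-10 walk a Week 6 value. An intention to count any early walk does not fit the claim of analogous handling, nor the plain reading of category 3.

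Three stronger readings are tempting.
- **The confirmatory analyses are compromised.** They are not. Their Week 12 window opens on day 78, and an earlier value enters only below all measured values, for patients without a clinical event.
- **Weight and haematology lose a death or event ranking too.** They have none; they are analysed by ANCOVA.
- **Early weight and haematology values pull those estimates towards zero.** The documents do not show this. Protocol Section 1.3 says effects begin with the first dose or within the first few weeks. A returning patient's Week 12 weight replaces the early one, because SAP Section 7.6 uses all data. For laboratory summaries, SAP Section 7.8.2 already reports the last value on treatment. An early on-treatment haemoglobin or haematocrit sample can still stand after a return visit, because that ANCOVA uses on-treatment data only.

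**Conclusion.** The point holds for the Week 6 walk distance. As written, a single walk in the first days, with no later walk in the window, counts as a measured Week 6 result and takes precedence over death or an adverse-event stop before the protocol visit. That conflicts with category 3 of Table 6.6.3:1 and with the primary-endpoint handling it is said to follow.

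The size is unknown, because the documents give neither early-stop rates nor a Week 6 effect. It is about 1 to 4 power points if stops are balanced at an assumed 5 to 10% per arm. The 20-to-28-point figures need an assumed 8% against 2% imbalance with no later in-window walk for any stopper, so they are illustrations and not forecasts. The argument for changing the rule is consistency, not power.

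It is also unclear which window end applies. Table 6.7:1 and the SAP history table point to day 77 for Wilcoxon models, while the Section 6.7 text on all other endpoints points to day 64. Both windows open on day 2, so the finding does not depend on this.

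The weight, haemoglobin and haematocrit window is a minor labelling matter: an early value can be presented as Week 12, with no shown direction of bias.

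**What to change.** For the Week 6 walk analysis:
1. Open the window on day 36, the protocol-minus-7-days rule already used for Week 12 in Table 6.7:1.
2. Add the last-available-value row of Protocol Table 7.5:1 (−352 + x/1000) to Table 6.6.3:1 for patients whose only walk is earlier and who had no clinical event. Apply categories 2 and 3 to those with a clinical event or death.
3. Restate the Week 6 dates in footnote 2 of Table 6.7:1 to match the new window, and say whether it ends on day 77 or day 64.

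For endpoints not taken at Visit 3, either set a lower bound, for example the baseline/Week 12 midpoint at about day 43, or label the result as last value on treatment. Opening on day 65 would borrow the midpoint with Visit 3, at which these endpoints are not assessed, so it does not follow from the SAP's algorithm.

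These are SAP table edits and need no new data; they should be made before unblinding. The cost is a few more imputed patients at Week 6 and, if the lower bound is chosen, a few early weight and haematology values no longer counted as Week 12.

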6.2.3 Follow up period and trial completion

A follow up visit will be performed 7 days (+7 day window) after the last dose of trial medication. The assessments to be performed at the follow-up visit are indicated in the [Flow Chart](#). The follow-up visit marks the completion of the study for the individual patient.

See [section 3.3.4.1](#) for procedures to be followed in case a patient prematurely discontinues trial treatment.

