7.6 FURTHER ENDPOINTS

All further endpoints will take into account all data, regardless of whether the patient was on treatment or not, and without imputation of missing values (OC-AD).

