7.6.3 Continuous endpoints

Further continuous endpoints are generally analysed in a mixed model with repeated measures (MMRM), including visit-by-treatment interaction and baseline-by-visit interaction. An unstructured covariance structure will be used to model the within-patient errors. The MMRM analyses will also be shown graphically.

Descriptive statistics will be calculated for the value at visit and change from baseline.

- Change from baseline in KCCQ overall summary score, CSS, and individual domains at Week 6 and week 12
- Change from baseline in CHQ individual domains at week 6 and week 12
- Change from baseline in SBP at Week 6 and week 12
- Change from baseline in DBP at Week 6 and week 12

The following endpoint is assessed as part of the main analysis or sensitivity analysis of the corresponding secondary endpoint:

- Change from baseline in KCCQ TSS at Week 6
- Change from baseline in CHQ-SAS dyspnea at Week 6
- Change from baseline in Clinical Congestion Score at week 6.
- Change from baseline in NT-proBNP at week 6.

Since bodyweight is only measured at baseline and week 12, an ANCOVA model will be presented including baseline weight as a covariate.

Descriptive statistics are planned for:

- Change from baseline to week 6 and week 12 in patient-rated assessment of dyspnea and fatigue by the Borg scale as part of the 6MWT

For the following parameters measured at the follow-up visit, additionally descriptive statistics at baseline, last value on treatment and follow-up will be presented for patients with valid measurements at all three timepoints. .

- SBP
- DBP

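### In the OC-AD analysis, the Week 12 blood pressure of a completer with an early Visit 4 (days 78 to 81) can be taken from the off-drug follow-up visit, and the SAP's pointers to the window tables conflict

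*SAP*

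**What the plan says.** SAP 6.7 states for OC-AD that "all post-randomisation (for OC-AD analysis) efficacy and safety measurements will be assigned to visits based on time windows". The OC-AD table (Table 6.7:3) is titled "Time windows for measurements except primary analysis of primary and key secondary endpoints [OC-AD", followed by a closing bracket. Its Week 12 row reads "4 | Week 12 | 85 | +65 | NA": planned day 85, start day 65, no end. It has no follow-up row. The on-treatment table (Table 6.7:2, OC-OT) ends Week 12 at treatment stop plus an endpoint-specific number of days and does have a follow-up row.

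Within a window, "the value will be selected which is closest to the protocol planned visit day". The tie rule begins "If there are two measurements which have the same time difference in days to the planned day" and gives the first value.

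Blood pressure comes under these rules as follows. SAP 4.1 adds SBP and DBP, and SAP 7.6.3 lists "Change from baseline in SBP at Week 6 and week 12" with a matching line for DBP. SAP 7.6 says "All further endpoints will take into account all data, regardless of whether the patient was on treatment or not", that is, OC-AD. The protocol flow chart has vital signs at Visit 4 and at follow-up. Protocol 6.2.3: "A follow up visit will be performed 7 days (+7 day window) after the last dose of trial medication".

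Two places point elsewhere. SAP 6.6.4 sends OC-AD measurements to Tables 6.7:1 and 6.7:2, and the paragraph before Table 6.7:1 refers all other endpoints to Table 6.7:2.

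**The concern.** A completer can attend Visit 4 inside the allowed window, give a valid post-dose blood pressure, and still have that reading discarded. If Visit 4 is on day 78 and follow-up on day 85, Table 6.7:3 labels the reading taken a week after the last dose as Week 12. SAP Table 6.1:2 treats blood pressure as on-treatment for only one day after the last intake, so by the SAP's own definition the selected value is post-treatment.

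This differs from the deliberate OC-AD choice to keep off-drug values from early discontinuers. These patients finished treatment and have the scheduled value. At stake is the Week 12 SBP and DBP contrast. The protocol names blood pressure lowering among the drug's effects (sections 1.1 and 4.1.2), so the expected direction is dilution.

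**Working it through.** **Inputs.** Planned days 43 and 85, window start 65, open end, nearest-day rule and tie rule: SAP 6.7. Visit 4 on day 85 ± 7, that is days 78 to 92: protocol flow chart. Visit 4 is the last treatment day: protocol 6.2.2. Follow-up 7 to 14 days after the last dose: protocol 6.2.3.

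**The plan's own boundary.** The midpoint rule gives (43 + 85)/2 = 64, counted in the earlier visit, so Week 12 starts on day 65. This matches Table 6.7:3.

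**Which reading wins.** Let v be the Visit 4 day and g the gap to follow-up (7 to 14). Follow-up is selected when |v + g − 85| < |v − 85|; a tie keeps Visit 4.

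| Visit 4 day | Distance from day 85 | Follow-up days that win | Of 8 allowed |
|---|---|---|---|
| 78 | 7 | 85 to 91 (92 ties) | 7 |
| 79 | 6 | 86 to 90 | 5 |
| 80 | 5 | 87 to 89 | 3 |
| 81 | 4 | 88 | 1 |
| 82 | 3 | none (earliest is day 89, distance 4) | 0 |
| 83 to 92 | – | none | 0 |

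If the last dose were the day before Visit 4 (g from 6 to 13), the exposed range would still be days 78 to 81.

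**How many completers.** The documents give no visit-day distribution, so these are illustrations.
- Visit 4 uniform over 15 days, follow-up uniform over 8 days: (7 + 5 + 3 + 1)/(15 × 8) = 16/120 = 13%.
- Visit 4 uniform, every follow-up at exactly +7 days: 4/15 = 27%.
- Visit 4 normal around day 85 with SD 3 days, rounded to whole days and limited to days 78 to 92: probabilities for days 78 to 81 are 0.0090, 0.0185, 0.0339 and 0.0556. With uniform follow-up: 0.0090 × 7/8 + 0.0185 × 5/8 + 0.0339 × 3/8 + 0.0556 × 1/8 = 0.039, about 4%. With every follow-up at +7 days: the four sum to 0.117, about 12%.

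**Effect on the contrast.** Let f be the affected fraction (taken as equal in both arms and unrelated to outcome), r the share of the blood pressure effect lost by follow-up, and δ the on-drug difference. The expected Week 12 difference is about (1 − f)δ + f(1 − r)δ = δ(1 − f·r). With r = 1 the shrinkage is f; with r below 1 it is smaller. The documents give no value for r.

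**Which endpoints are exposed.** The flow chart shows no 6MWT, KCCQ, CHQ-SAS, global impression, congestion score, NT-proBNP or weight at follow-up. Creatinine, eGFR, haemoglobin, haematocrit and heart rate are analysed on OC-OT (SAP 7.8.2 and 7.8.3). That leaves SBP and DBP.

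**The alternative pointer.** Under Table 6.7:2, Week 12 for blood pressure ends one day after treatment stop, so a completer's follow-up reading cannot become Week 12. But a patient who stops early and returns for the scheduled week 12 visit (protocol 3.3.4.1) would then have that visit placed under follow-up, which defeats OC-AD as SAP 6.6.4 defines it.

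**The case against.** The strongest reply is that SAP 6.6.4 and the paragraph before Table 6.7:1 lead to a table with a follow-up row, so the replacement may never have been intended. The selection sentence also speaks of an on-treatment visit, and the SAP elsewhere treats follow-up as its own timepoint for SBP and DBP. This stands as far as it shows inconsistent text: a reader might infer that the SAP unambiguously prescribes the replacement, and it does not. The reply does not remove the problem. Table 6.7:3 carries the OC-AD label, the text below it names it for OC-AD analyses, no sentence excludes follow-up readings, and Table 6.7:2 cannot deliver OC-AD for early discontinuers.

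A second reply is that the larger percentages are extreme. That also stands. The 27% needs Visit 4 spread evenly over the whole window and every follow-up at exactly seven days. Protocol 6.1 keeps visits tied to the original schedule, which makes clustering near day 85 more plausible.

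Third, barring follow-up readings from Week 12 altogether would contradict OC-AD's inclusion of all available data. Suppose a patient has a discontinuation visit on day 70, follow-up on day 80, and only a phone contact at week 12. Day 80 is nearer day 85 and is a legitimate OC-AD value. This stands, and the remedy should be narrower.

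**Conclusion.** The point holds in limited form. Read with Table 6.7:3, the SAP lets an off-drug follow-up blood pressure replace the on-drug Visit 4 value in completers whose Visit 4 falls on days 78 to 81, and never when it falls on days 82 to 92. Read with the pointer to Table 6.7:2 it does not, but early discontinuers' Week 12 visits are then lost from Week 12. The passages must be reconciled.

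The likely size is about 4-12% of completers with Visit 4 clustered around day 85 (SD 3 days), and 13-27% if it is uniform. Dilution of the Week 12 difference is at most about that fraction, and reaches it only if the effect is fully lost by follow-up. All of this rests on assumed visit timing.

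Two wider inferences are not supported. The primary, key secondary and other secondary endpoints are untouched, because none is measured at follow-up. The baseline / last-on-treatment / follow-up display in SAP 7.6.3 is also unaffected: it uses the last on-treatment and follow-up values, not the OC-AD Week 12 value. The consequence is confined to exploratory blood pressure analyses.

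**What to change.** Correct the cross-references in SAP 6.6.4 and in the paragraph before Table 6.7:1 so that OC-AD analyses use Table 6.7:3. Add to Table 6.7:3 that when a Visit 4 (scheduled Week 12) measurement exists it is the Week 12 value, on or off drug, and a scheduled follow-up measurement cannot replace it. Where there is no Visit 4 measurement, leave the nearest-day rule as it is, so that post-treatment readings remain available.

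The cost is a small programming change and use of the visit label alongside the day window. No new data are needed, and no confirmatory analysis changes.
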